6.9. Concomitant Therapy and eCOA Compliance

The summary and reporting of concomitant therapy and eCOA compliance has been described in the CPMP SAP Version 5. No additional covariates will be considered in the model of weekly rescue medication use.

Concomitant therapy will be reported for the first 4 weeks of the double-blind period (active-treatment phase) and separately for the entire 8 weeks of the double-blind period.

6.10. Efficacy Analyses

6.10.1. Primary Outcome and Methodology

The analysis of the primary outcome has been described in the CPMP SAP Version 5. The longitudinal model will include API-NRS during the preliminary data-entry period (PDEP, last 7 days prior to randomization at Visit 3) and within each nominal week of the double-blind treatment period as a longitudinal outcome. As noted in Section 4.1, the endpoint for the primary analysis is defined as 4 weeks post initial treatment administration.

Calculation of the weekly or biweekly time intervals used for analysis of weekly or biweekly mean scores from the eCOA device will follow the algorithm described in the Study CPMP SAP Section 6.12.1, except that the end of the final interval will be determined based on the last visual analog scale (VAS) result collection date or the last scheduled visit start date if VAS results are missing for the last scheduled visit.

6.10.2. Additional Analyses of the Primary Outcome

Borrowing placebo information by pooling from Studies H0P-MC-OA01 and H0P-MC-OA03 for the evaluation of treatment effect on the mean change from baseline of API-NRS (and secondary outcomes of worst pain intensity as measured by the NRS, WOMAC® pain subscale, and VAS) will be performed following the description in CPMP SAP Version 5, Section 6.12.1. Descriptive statistics of primary outcome variables by demographics, disposition, disease characteristics, and treatment administration may be summarized by ISA to examine the population homogeneity assumption between ISAs.

6.10.3. Secondary Efficacy Analyses

Secondary efficacy analyses common to all ISAs within CPMP have been described in the CPMP SAP Version 5. Unless otherwise specified, the time point for secondary endpoint measurements is the same as that for the primary endpoint. Study OA02 will also consider the following secondary analyses.

The Western Ontario and McMaster Universities Osteoarthritis Index (Bellamy 2005) is a validated instrument that is extensively used to evaluate the response to medications for the treatment of osteoarthritic pain. The WOMAC® version LK3.1 will be administered according to the Schedule of Activities.

This 24-question WOMAC® and its subscales are described as follows.

Dimensions/Subscales	Number of Questions
pain	5
stiffness	2
physical function	17

The participants will record their responses using a 0 to 4 Likert scale for each question:

0 = no pain (or stiffness or difficulty), and

4 = extreme pain (or stiffness or difficulty).

The scores for each subscale will be calculated by summing the scores of the questions in the respective subscale for each participant at each time point.

The range of possible scores for each subscale is pain = 0 to 20, stiffness = 0 to 8, and physical function = 0 to 68.

6.10.3.1. Key Secondary Analysis

A Bayesian longitudinal mixed-model repeated measures analysis (MMRM) will be performed to evaluate the change from baseline to each postbaseline visit for the WOMAC® pain subscale, physical function subscale, and stiffness subscale. The model will utilize the constrained cell means model so that a common mean is estimated at baseline. More details on this approach are provided in the CPMP SAP Version 5.

Information included in the model is described as follows.

Categorical factors	the interaction of treatment and time point (constrained to estimate a common mean at baseline across treatments) average baseline pain severity category (baseline NRS < 7, baseline NRS ≥ 7) pooled investigative site
Continuous covariates	none

Abbreviation: NRS = Numeric Rating Scale.

6.10.3.2. Other Secondary Analysis

The proportion of participants in each treatment group meeting prespecified binary response thresholds (30%, 50%, 70%) will be calculated for each postbaseline time point and will be used to compare treatment groups for WOMAC® pain and physical function subscales.

A Bayesian pseudo-likelihood based categorical repeated measures model will be used to estimate the proportion of participants in each treatment group meeting the prespecified threshold for each postbaseline time interval up to Week 4 (or visit up to Visit 5) and separately up to Week 8 (or visit up to Visit 7). These estimates will be used to compare treatment groups. More details on this approach are provided in the CPMP SAP Version 5.

The model will include the categorical and continuous covariates described for the key secondary analysis.

In addition, time to first treatment response from baseline based on the prespecified binary thresholds above will be assessed. Analyses will be conducted according to the time to event analyses specified in the CPMP SAP Version 5.

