4.2. Secondary Objectives

Secondary objectives applicable to all ISAs are listed in the H0P-MC-CPMP (CPMP) SAP Version 5.

The key secondary objective for Study OA02 is to evaluate whether LY3526318 is superior to placebo in reducing pain as measured by the mean change from baseline assessment to Week 4 for pain intensity measured by the Western Ontario and McMaster University Arthritis Index (WOMAC®) pain subscale.

Additional secondary endpoints specific to Study OA02 are listed below.

Objective	Endpoint Measure
Other Secondary	
Efficacy of LY3526318 versus placebo for overall improvement	Mean change from baseline assessment to 4 weeks for overall improvements as measured by the Patient Global Impression of Change
Efficacy of LY3526318 versus placebo	Mean change from baseline to endpoint on the WOMAC® stiffness and physical function subscale Proportion of participants with reduction from baseline greater than or equal to 30%, 50%, and 70% on the WOMAC® pain subscale at each time point Proportion of participants with reduction from baseline greater than or equal to 30%, 50%, and 70% on the WOMAC® physical function subscale at each time point

Abbreviation: WOMAC = Western Ontario and McMaster University Arthritis Index.

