5.2. Determination of Sample Size

Approximately 150 participants will be randomized in a **CCI** ratio to LY3526318 and placebo. It is expected that approximately 85% or 128 participants will complete the double-blind treatment period of the study. **CCI**

CCI

If there is no treatment difference between placebo and LY3526318, the probability of passing the efficacy criterion specified above (that is, false positive) is less than 0.1. The simulation for the power calculation and sample size determination was carried out using the Fixed and Adaptive Clinical Trial Simulator (FACTS) Version 6.0.

CCI

If there is no treatment difference between placebo and LY3526318, the probability of passing the efficacy criterion specified above for average pain intensity (that is, false positive) is approximately 0.1.

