6.2. Adjustments for Covariates

The general adjustment strategy has been described in the CPMP SAP Version 5.

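### The WOMAC responder models inherit a covariate list written for a common-baseline MMRM, so as written they do not adjust for the baseline score of the subscale analysed

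*SAP*

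**What the plan says.** SAP 4.2 lists responder endpoints among the other secondary endpoints: "Proportion of participants with reduction from baseline greater than or equal to 30%, 50%, and 70% on the WOMAC® pain subscale", and the same for physical function, at each time point. SAP 6.10.3.2 analyses them with a Bayesian pseudo-likelihood categorical repeated measures model for postbaseline intervals, up to Week 4 and separately up to Week 8. The estimated proportions are used to compare the arms. The covariates are given by reference only: "The model will include the categorical and continuous covariates described for the key secondary analysis".

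The list referred to is in SAP 6.10.3.1. It has three categorical entries:
- treatment by time point, "constrained to estimate a common mean at baseline across treatments"
- baseline NRS severity category (below 7, or 7 and above)
- pooled investigative site

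The continuous entry is "Continuous covariates none". The same section explains how baseline WOMAC is handled in the MMRM: "The model will utilize the constrained cell means model so that a common mean is estimated at baseline".

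SAP 6.2 adds only: "The general adjustment strategy has been described in the CPMP SAP Version 5". Section 6.10.3.2 also refers to that document for more detail on the responder approach.

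**The concern.** The entry for continuous covariates means different things in the two models. In the MMRM it does not mean that baseline is ignored. Baseline WOMAC is part of the outcome vector, and its covariance with later visits sharpens the treatment contrast. In the responder model baseline cannot be an outcome, so the same entry means that no continuous baseline score is used. The cross-reference therefore loses an adjustment that the MMRM has, and it brings in a baseline constraint that cannot be applied.

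What is at stake is precision on the WOMAC pain and physical function responder comparisons. No bias or type I error problem arises, and the primary and key secondary analyses are untouched.

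**Working it through.** **1. What carries over.**

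| Item in SAP 6.10.3.1 | MMRM on subscale score | Responder model (SAP 6.10.3.2) |
|---|---|---|
| Treatment by time point, common mean at baseline | Baseline score is a response; constraint applies | Percentage reduction at baseline is zero for everyone; nothing to constrain |
| Baseline NRS category | Applies | Applies, but is a two-level split of a different instrument |
| Pooled site | Applies | Applies |
| Continuous covariates: none | Baseline WOMAC already used through the covariance | Baseline WOMAC not used as a covariate |

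Baseline WOMAC still enters the responder endpoint as the denominator of the percentage reduction.

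**2. Does the denominator already do the work?** A participant responds at threshold t if the Week 4 score is at most (1 − t) × baseline. Let r be the baseline-to-Week 4 correlation. Ignoring rounding and scale limits, the responder margin, (1 − t) × baseline minus the Week 4 score, has this slope on baseline:

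(1 − t) − r × SD(Week 4)/SD(baseline)

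It is zero when r = (1 − t) × SD(baseline)/SD(Week 4). With assumed pain SDs of 3.5 at baseline and 4.5 at Week 4:
- 30%: 0.7 × 3.5/4.5 = 0.54
- 50%: 0.5 × 3.5/4.5 = 0.39
- 70%: 0.3 × 3.5/4.5 = 0.23

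No single correlation removes the dependence at all three thresholds. Gains should be small in the middle range of r and larger away from it.

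**3. Size, by simulation.**

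From the documents: 128 completers (SAP 5.2; 0.85 × 150 = 127.5, rounded up to 128), the thresholds of 30%, 50% and 70%, and the score ranges of 0 to 20 and 0 to 68.

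Assumed, because the documents give no values:
- Pain: baseline mean 11, SD 3.5; Week 4 placebo mean 8, SD 4.5; effect 1.5.
- Physical function: baseline mean 36, SD 11; Week 4 placebo mean 26, SD 15; effect 4.5.
- r = 0.1, 0.3, 0.5, 0.7 and 0.8; latent correlation of NRS category with baseline WOMAC 0.5; 6 pooled sites.
- Allocation 1:1 and 2:1 (the ratio is redacted).
- WOMAC at Weeks 2 and 4 (the schedule in the OA02 protocol does not show WOMAC visits).

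This gives 5 × 3 × 2 × 2 = 60 scenarios, each with 4,000 replicates. The model was a working-independence logistic pseudo-likelihood with weak normal priors, always containing NRS category and site, fitted with and without the baseline score. It approximates the planned model and is not a replica. The estimate was the Week 4 difference in standardised proportions.

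Gain = (empirical variance without baseline / empirical variance with baseline) − 1

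| r | Change in effective sample size | 128 completers become equivalent to |
|---|---|---|
| 0.1 | -0.6% to +11.1% | 127 to 142 |
| 0.3 to 0.5 | -1.1% to +4.6% | 127 to 134 |
| 0.7 | +1.8% to +16.7% | 130 to 149 |
| 0.8 | +7.2% to +31.0% | 137 to 168 |

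The last column is 128 × (1 + gain). The Monte Carlo standard error of the gain was 0.3 to 2.2 percentage points. Mean differences with and without baseline agreed within 0.001, so both fits estimate the same quantity.

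**4. The same effect seen as chance imbalance.** Without the covariate, a one-standard-error baseline imbalance moves the responder difference by 0.0 to 1.7 percentage points at r = 0.3 to 0.5 and by 1.9 to 3.1 points at r = 0.8. The standard error of that difference is 6.3 to 9.4 points.

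**5. Cross-checks.** A Week 4-only run (pain, 1:1, 1,500 replicates, same inputs) gave about -1% to +2% at r = 0.3 to 0.5, +1% to +17% at 0.7 and +7% to +26% at 0.8. The assumed Week 2 visit therefore does not drive the result.

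A separate single-time-point logistic simulation used different assumed inputs (pain baseline SD 3.3, follow-up SD 4.0, effect 1.8; 600 runs per scenario; 30% and 50% thresholds). Power changed by about -0.5 to +3 points at r = 0.2 to 0.6. At r = 0.8 and the 50% threshold it rose by 8 to 8.5 points (0.72 to 0.81 at 1:1; 0.66 to 0.74 at 2:1). In that 1:1 case the mean log odds ratio also moved, from 1.12 to 1.34, because the odds ratio is conditional on the covariates.

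**The case against.** The strongest reply is that the OA02 SAP is a supplement. It leaves the general adjustment strategy and the detail of the responder approach to CPMP SAP Version 5, which may already add the baseline score. That possibility stands. However, 6.10.3.2 has its own explicit covariate sentence pointing to a list with no continuous covariate. If the master SAP adds baseline, the two texts need reconciling; if it does not, the omission is real.

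Second, leaving a prognostic covariate out of a supportive analysis is a legitimate choice. The model already adjusts for NRS category and site, and the continuous WOMAC analyses use baseline efficiently. This also stands, and it is why the point is minor.

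Third, the gain is close to zero at mid-range correlations, and no document gives the correlation, so +31.0% is not an expected value. That is correct.

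Fourth, any statistician would drop the baseline constraint and fit treatment by postbaseline time. Probably so, but the text should say it.

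Fifth, asking for standardised proportions goes beyond the omission, and the effect measure may be set in the CPMP SAP. Yet 6.10.3.2 already bases the comparison on estimated proportions. Without standardisation, adding a covariate would change the meaning of an odds ratio.

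**Conclusion.** The point holds as a statement about the OA02 SAP as written: the responder models inherit a list that omits the baseline subscale score and contains a constraint with no meaning for them. The consequence is possible loss of precision on other secondary endpoints. Under the assumed inputs the effect of adding baseline is negligible at correlations of 0.3 to 0.5 and worthwhile at 0.7 to 0.8, and the worst simulated loss is 1.1%. These sizes depend on the assumed means, SDs, correlations and allocation. Confidence is medium, because CPMP SAP Version 5 could not be checked. It is a desirable improvement, not a required correction.

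**What to change.** In SAP 6.10.3.2, replace the inherited sentence with an explicit list for the responder models:
- treatment, postbaseline time point, and treatment by postbaseline time point
- average baseline pain severity category (baseline NRS < 7, ≥ 7)
- pooled investigative site
- continuous baseline score of the WOMAC subscale being analysed

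Add that the treatment comparison is reported as a difference in model-standardised proportions, so that the covariate does not change the quantity estimated.

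If CPMP SAP Version 5 already includes the baseline score, cite that section instead of the key secondary list. If the score is left out on purpose, say so.

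The cost is two SAP sentences. Baseline WOMAC is already needed to compute the endpoint, so no participants, visits or procedures are added.

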6.11. Bioanalytical and Pharmacokinetic/Pharmacodynamic Methods

The observed plasma concentrations for LY3526318 over time will be reported in tabular format using descriptive statistics and graphically using individual and mean concentration time plots.

Nominal protocol time will be used for the descriptive summary and mean plot and actual time for the plots of individual data.

Additional analyses may be conducted as deemed necessary on review of the data. For example, graphical and/or model-based pharmacokinetic (PK) and PK-pharmacodynamic (PD) analyses to explore exposure-response relationships for safety and/or efficacy may be conducted. Data from this study may be pooled with data from other studies if appropriate.

6.12. Safety Analyses

The general analysis of safety has been described in the CPMP SAP Version 5. However, additional ISA-specific safety considerations are described in the sections below.

6.12.1. *Extent of Exposure*

Duration of exposure (defined as time since first dose of study treatment to last dose of study treatment in days) to study drug will be summarized by treatment group using descriptive statistics; the summary will also include the total exposure in patient years. Extent of exposure will be reported separately for the first 4 weeks (active treatment) and the last 4 weeks (post active treatment) of the double-blind period. All patients will receive placebo starting the day of Visit 5.

Duration of exposure (days):

For the first 4-week, active-treatment period:

= Date of last dose during the active treatment period Date of first dose for the active treatment period + 1.

For the last 4-week, post active-treatment period:

= Date of last dose during the post active-treatment period Date of first dose for the post active-treatment period + 1.

Total exposure in patient years will be calculated as follows:

Total exposure in patient years = Sum of duration (days) of exposures for all patients in the treatment group/365.25.

6.12.2. *Adverse Events*

The general analysis of AEs has been described in the CPMP SAP Version 5.

This ISA will report TEAEs for the first 4 weeks as well as post treatment-emergent AEs (PTEAEs) for the last 4 weeks of the double-blind period. For TEAEs in the first 4 weeks of the double-blind period (active-treatment phase), the baseline will be prior to the first dose date.

A PTEAE is defined as an event that first occurs or worsens in severity after the active-treatment phase (after Visit 5) and on or before study discontinuation. The Medical Dictionary for Regulatory Activities (MedDRA) Lowest Level Term (LLT) will be used in the post treatment-emergent computation. The maximum severity for each LLT during the active-treatment period (Visits 3 to 5) will be used as a reference.

The baseline of PTEAE is from the first dosing date to Visit 5. The post active-treatment phase (after Visit 5) will be included as postbaseline for this analysis. While unusual, it is possible to have a missing severity for events. For an event with a missing severity during the baseline

Events with a missing severity during the post-active-treatment period will be treated as

, , , PTEAEs will be determined by comparing with the active-treatment period.

PTEAEs will be summarized by Preferred Term and by Preferred Term within System Organ Class in participants who received LY3526318.

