6.1. General Considerations

The estimand for the primary clinical question of interest has been described in the CPMP SAP Version 5.

The key secondary clinical question of interest is: What is the treatment difference between LY3526318 and placebo assessed using mean change from baseline to Week 4 for pain as measured by the WOMAC® pain subscale in participants with osteoarthritis of the knee regardless of initiation of rescue medication or other allowed concomitant medication and assuming that they would have continued initially randomized treatment condition?

Treatment condition: the randomized treatment along with potential use of rescue medication or other allowed concomitant medications regardless of adherence.

Population: participants with chronic pain conditions.

Endpoint: change from baseline to Week 4 in the WOMAC® pain subscale.

Intercurrent events: the intercurrent event is treatment discontinuation for any reason.

Population-level summary: difference in mean changes from baseline between treatment conditions.

The estimand is following a hypothetical strategy where efficacy of LY3526318 is assessed under the assumption that the participants would have continued their initially randomized treatment condition even if they discontinued.

Unless otherwise specified, efficacy analyses will be conducted for the first 4 weeks of the double-blind period (active-treatment phase) and separately for the entire 8-week study. A post active-treatment population will be used for analyses of the last 4 weeks of the double-blind period (post active-treatment phase) and will include all patients who do not discontinue at or prior to Visit 5. For treatment-emergent adverse events (TEAEs), participants in the post active-treatment population will be analyzed according to the treatment they receive during the active-treatment phase. Adverse event (AE) analyses will be reported for the first 4 weeks of the double-blind period (active-treatment phase) and separately for the last 4 weeks of the double-blind period (post active-treatment phase). Some AEs may be reported for the entire 8 weeks if necessary. Laboratory, electrocardiogram, and vital sign results will be reported for the active-treatment phase and separately for the entire 8-week study.

Other general considerations for analyses are described in the CPMP SAP Version 5.

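### The tables of adverse events arising after Visit 5 are planned for LY3526318 recipients alone, although a randomized placebo group is followed over the same four weeks

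*SAP*

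**What the plan says.** SAP section 5.1 gives the LY3526318 arm active drug for four weeks and then placebo from the day of Visit 5. The placebo arm takes placebo throughout the eight weeks.

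Section 6.12.2 divides adverse event reporting at that switch: "This ISA will report TEAEs for the first 4 weeks as well as post treatment-emergent AEs (PTEAEs) for the last 4 weeks". A PTEAE is an event that first occurs or worsens after Visit 5, judged against the earlier period: "The maximum severity for each LLT during the active-treatment period (Visits 3 to 5) will be used as a reference". On the tables themselves the section says: "PTEAEs will be summarized by Preferred Term and by Preferred Term within System Organ Class in participants who received LY3526318".

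Section 6.1 is broader. It defines a post active-treatment population that "will include all patients who do not discontinue at or prior to Visit 5". It adds: "For treatment-emergent adverse events (TEAEs), participants in the post active-treatment population will be analyzed according to the treatment they receive" during the active phase. It also plans adverse event analyses for the last four weeks without naming one arm, and leaves a whole-period display optional: "Some AEs may be reported for the entire 8 weeks if necessary".

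Section 6.12.1 keeps both arms for exposure. Duration of exposure "to study drug will be summarized by treatment group using descriptive statistics", and "Extent of exposure will be reported separately for the first 4 weeks (active treatment) and the last 4 weeks (post active treatment").

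**The concern.** Events in Weeks 4 to 8 in the LY3526318 arm mix possible effects of stopping the drug, late effects of having taken it, and the ordinary background of a knee osteoarthritis population seen at regular visits. The natural yardstick for the background is the randomized placebo arm, observed under the same blinded conditions over the same weeks. The PTEAE definition depends only on calendar position relative to Visit 5 and on earlier severity, so it can be applied unchanged to placebo participants.

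A table limited to LY3526318 recipients sets that yardstick aside. Its reader sees a list of events that began or worsened after the switch, with no rate beside it to show how many would be expected anyway. At stake is the interpretation of two descriptive safety tables.

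**Working it through.** **Sections set side by side**

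| SAP section | Arms covered in the last four weeks |
|---|---|
| 5.1 design | both followed, both on placebo |
| 6.1 population | all who have not discontinued by Visit 5 |
| 6.1 grouping rule | by active-phase treatment, worded for TEAEs |
| 6.12.1 exposure | by treatment group |
| 6.12.2 PTEAE tables | LY3526318 recipients |

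Sections 6.1 and 6.12.2 do not flatly contradict each other. Section 6.1 states its by-arm rule for TEAEs, while 6.12.2 assigns TEAEs to the first four weeks and PTEAEs to the last four. Whether the rule was meant to reach PTEAEs is left open.

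**Inputs for the illustration**

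- About 150 randomized and 128 expected to complete (section 5.2). Check: 150 × 0.85 = 127.5, which agrees with 128.
- The post active-treatment population should lie between these two figures if dropout is as planned.
- The allocation ratio is redacted. Assumed splits (LY3526318:placebo) are 64:64 and 75:75 for 1:1, and 85:43 and 100:50 for 2:1.
- Background PTEAE rates over four weeks are not given. Assumed values are 2% and 5% for a single term, and 10% and 30% for any PTEAE.

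**Expected LY3526318 participants with an event when the drug has no effect (n × p)**

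| p | n = 64 | 75 | 85 | 100 |
|---|---|---|---|---|
| 2% | 1.3 | 1.5 | 1.7 | 2.0 |
| 5% | 3.2 | 3.8 | 4.3 | 5.0 |
| 10% | 6.4 | 7.5 | 8.5 | 10.0 |
| 30% | 19.2 | 22.5 | 25.5 | 30.0 |

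For one term, the binomial chance that background alone puts at least two LY3526318 participants in the table is 0.37 (2%) to 0.84 (5%) with n = 64, and 0.51 to 0.93 with n = 85.

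**What a placebo column would add**

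Half-width of the 95% interval for the risk difference, in percentage points, with rate p in both arms: 100 × 1.96 × √[p(1−p)(1/n₁ + 1/n₂)]. Example at 10% and 64:64: 196 × √(0.09 × 2/64) = 10.4.

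| p | 64:64 | 75:75 | 85:43 | 100:50 |
|---|---|---|---|---|
| 2% | 4.9 | 4.5 | 5.1 | 4.8 |
| 5% | 7.6 | 7.0 | 8.0 | 7.4 |
| 10% | 10.4 | 9.6 | 11.0 | 10.2 |
| 30% | 15.9 | 14.7 | 16.8 | 15.6 |

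Chance that the 95% Wald interval excludes zero (normal approximation, unpooled standard error). Example for 20% v 10% at 64:64: SE = √(0.16/64 + 0.09/64) = 0.0625, so 0.10/0.0625 = 1.60 and the chance is about 0.36.

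| LY3526318 v placebo | 64:64 | 75:75 | 85:43 | 100:50 |
|---|---|---|---|---|
| 20% v 10% | 0.36 | 0.41 | 0.35 | 0.40 |
| 30% v 10% | 0.83 | 0.89 | 0.84 | 0.89 |
| 40% v 30% | 0.22 | 0.25 | 0.21 | 0.23 |

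**A caution for any two-arm table**

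The severity reference period is on drug in one arm and on placebo in the other. Suppose a term has active-phase rates of 20% (LY3526318) and 5% (placebo) and a true post-period rate of 10% in both, with independence and equal severity. An event already seen at that severity is not a PTEAE, so the PTEAE rates become 0.10 × 0.80 = 8.0% and 0.10 × 0.95 = 9.5%. The definition alone creates a small difference, which calls for a footnote.

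**The case against.** Section 6.12 supplements the master protocol's SAP (CPMP SAP Version 5), which is not supplied and is said to hold the general adverse event analysis and the full summary. The LY3526318 tables may sit on top of by-arm tables that already exist there. The word only does not appear in the sentence at issue. The post active-treatment population in section 6.1 has no evident use outside the last four weeks, so its grouping rule arguably must concern events in that period, and the gap would then be one of terminology. Section 6.17 may report key safety events for the post-active period. The registry summary in section 6.19 gives serious events by treatment group whether or not treatment emergent. It admits non-serious events if they are TEAEs, and on the protocol's general definition of a TEAE, placebo events in Weeks 4 to 8 might qualify.

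Much of this stands as a limit on the consequence. It cannot be said that readers will have no placebo adverse event data for the last four weeks. It does not remove the point. The plain meaning of the sentence is a one-arm table, section 6.17 is optional and covers listed events, the registry reading depends on a definition the SAP does not settle, and no supplied section commits to placebo PTEAEs by term.

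The figures also rest on assumed splits. A 3:1 allocation, 96:32 among completers, gives half-widths of 8.7, 12.0 and 18.3 points at 5%, 10% and 30%, and a chance of about 0.32 for 20% v 10%. Wald intervals are rough at 2% to 5%, where only about 1 to 5 events are expected. Both facts strengthen the view that the comparison is descriptive.

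**Conclusion.** The point holds, and it is minor. As written, the two PTEAE tables in section 6.12.2 omit a concurrent randomized control that the design provides, that belongs to the section 6.1 population, and that can be scored with the same definition.

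The benefit of adding it is context. A large imbalance such as 30% v 10% would usually show (0.83 to 0.89 for the 1:1 and 2:1 splits). A moderate one such as 20% v 10% usually would not (0.35 to 0.41). These figures depend on the assumed allocation, rates and population size. The finding itself depends only on the text. Whether CPMP SAP Version 5 already fills the gap cannot be judged from the supplied documents. No efficacy conclusion or error rate is affected.

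**What to change.** Before unblinding:

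- In section 6.12.2, replace the restriction to LY3526318 recipients with a summary by treatment group (LY3526318 and placebo) in the post active-treatment population, using one PTEAE definition for both arms.
- In section 6.1, state that the by-arm rule covers PTEAEs as well as TEAEs.
- Label the comparison descriptive. Add a footnote that the population leaves out participants who discontinued at or before Visit 5, and that the severity reference period is on drug in one arm and on placebo in the other.
- If a one-arm display is intended, say why in section 6.12.2 and name the output that reports placebo PTEAEs by term.

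The cost is one sentence, one clause, one placebo column in two tables and a footnote. No new data are needed.
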